8.2 Subject Accountability

The number of subjects screened and enrolled, and the number and percentage of subjects in each analysis set will be summarized. The number and percentage of subjects who complete each treatment period and of subjects who prematurely discontinue during each treatment period and the study will be summarized. The reasons for study discontinuation will also be summarized. A subject disposition listing will be provided for individual subjects.

8.3 Protocol Deviations

Major and minor protocol deviations will be summarized separately by type for the Full analysis set. The protocol deviations recorded in the CRF will be listed.

8.4 Demographics and Baseline Characteristics

Demographic characteristics and other baseline characteristics will be summarized descriptively for the Full Analysis Set and listed by subject including the following.

- Demographics: age, sex, race, ethnicity, height, weight, BMI, country and region
- Baseline Characteristics: baseline PD (serum phosphorus, etc.), renal ultrasound scores, baseline BPI-Q3, baseline skeletal survey radiographs measures, PHEX mutation

The summary of demographics and baseline characteristics will also be provided for the Primary Analysis Set when the number of subjects in the Primary Analysis Set is significantly fewer than the Full Analysis Set.

8.5 Disease Characteristics and Medical History

8.5.1 Medical History / XLH Medical History

Medical history will be summarized by body system for the Full Analysis set and will also be listed by subject. Fracture history will be summarized by reported term for the Full Analysis set and will also be listed by subject.

8.5.2 XLH Treatment History

The subjects' past XLH treatment with phosphates and vitamin D metabolites or analogs will be listed for the Full Analysis set if there is any reported XLH treatment history. For subjects receiving standard of care therapy for XLH (phosphate and/or vitamin D) the drug name, duration of treatment, dose and frequency of administration will be listed.

8.6 Efficacy Analysis

The primary efficacy analysis and other bone biopsy analysis (e.g. MAR, MS/BS, BFR, etc.) will be performed on the Primary Analysis set. All other efficacy analysis will be performed on the Full Analysis set at each milestone analysis. The treatment Extension Analysis Set might also be used for efficacy analysis at the final analysis.

8.6.1 Primary Efficacy Endpoint

The primary endpoint is the percent change from baseline at Week 48 in osteoid volume (osteoid volume/bone volume, OV/BV).

OV/BV at baseline, Week 48, both change from baseline, and percent change from baseline at Week 48 will be summarized. Change from baseline at Week 48 will be tested using a t-test if the normality assumption is valid. If the normal assumption is not met, a sign test will be used. The p-value from the statistical tests will be reported. A listing will be provided.

8.6.2 Key Secondary Efficacy Endpoint

The key secondary efficacy endpoint is the proportion of subjects achieving mean serum phosphorus levels above the LLN (2.5 mg/dL [0.81 mmol/L]) at the mid-point of the dose interval (i.e., Weeks 2, 6, 14, and 22), as averaged across dose cycles between baseline and Week 24.

The number and proportion of subjects achieving mean serum phosphorus levels above the LLN (2.5 mg/dL [0.81 mmol/L]) will be summarized and the two-sided 95% confidence interval will be provided for the proportion. The Wilson score method ([Wilson 1927](#)) will be

applied to estimate the confidence interval. The p-value for testing the proportion of subjects achieving the mean serum phosphorus levels above the LLN (2.5 mg/dL [0.81 mmol/L]) against 0% from the binomial test will also be provided.

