### Secondary Efficacy Objectives:

The key secondary efficacy objective is to establish the effect of KRN23 treatment on increasing serum phosphorus levels in adults with XLH

Other secondary efficacy objectives are to establish the effect of KRN23 treatment in adults with XLH on:

- Changes from baseline in additional histomorphometric parameters – including osteoid thickness (O.Th), osteoid surface/bone surface (OS/BS), and mineralization lag time (MLt)
- Changes from baseline in parameters of bone mineralization including mineral apposition rate (MAR), mineralizing surface (MS/BS), bone formation rate (BFR), and others
- Additional PD markers reflecting the status of phosphorus homeostasis and renal function
- Bone remodeling as assessed by bone turnover markers

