### 7.3.1 Inclusion Criteria

Individuals eligible to participate in this study must meet all of the following criteria:

- 1) Male or female, aged 18 - 65 years, inclusive
- 2) Diagnosis of XLH supported by classic clinical features of adult XLH (such as short stature or bowed legs), and at least ONE of the following at Screening:
  - Documented *PHEX* mutation in either the patient or in a directly related family member with appropriate X-linked inheritance
  - Serum iFGF23 level > 30 pg/mL by Kainos assay
- 3) Biochemical findings consistent with XLH based on overnight fasting (min. 8 hours):
  - Serum phosphorus < 2.5 mg/dL at Screening
  - TmP/GFR < 2.5 mg/dL at Screening
- 4) Presence of skeletal pain attributed to XLH/osteomalacia, as defined by a score of  $\geq 4$  on the Brief Pain Inventory question 3 (BPI-Q3, Worst Pain) at Screening. (Skeletal pain that, in the opinion of the investigator, is attributed solely to causes other than XLH/osteomalacia—for example, back pain or joint pain in the presence of severe osteoarthritis by radiograph in that anatomical location—in the absence of any skeletal pain likely attributed to XLH/osteomalacia should not be considered for eligibility.)
- 5) Estimated glomerular filtration rate (eGFR)  $\geq 60$  mL/min (using the Chronic Kidney Disease Epidemiology Collaboration [CKD-EPI] equation) or eGFR of 45 to <60 mL/min at Screening with confirmation that the renal insufficiency is not due to nephrocalcinosis
- 6) Provide written informed consent after the nature of the study has been explained, and prior to any research-related procedures. If the subject is a minor, provide written assent and have a legally authorized representative willing and able to provide written informed consent, after the nature of the study has been explained, and prior to any research-related procedures

- 7) Willing to provide access to prior medical records for the collection of biochemical and radiographic data and disease history
- 8) Females of child-bearing potential must have a negative urine pregnancy test at Screening and Baseline and be willing to have additional pregnancy tests during the study. Females considered not to be of childbearing potential include those who have not experienced menarche, are post-menopausal (defined as having no menses for at least 12 months without an alternative medical cause) or are permanently sterile due to total hysterectomy, bilateral salpingectomy, or bilateral oophorectomy.

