4.2 Key Secondary Efficacy Endpoint

The key secondary efficacy endpoint is the proportion of subjects achieving mean serum phosphorus levels above the lower limit of normal (LLN; 2.5 mg/dL [0.81 mmol/L]) at the mid-point of the dose interval (i.e., Weeks 2, 6, 14, and 22), as averaged across dose cycles between baseline and Week 24.

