8 STATISTICAL METHODS OF ANALYSIS

8.1 General Principles

The statistical analyses will be reported using summary tables, figures, and data listings. Statistical tests will be 2-sided at the $\alpha=0.05$ significance level and 2-sided 95% confidence interval will be used. All p-values will be presented as nominal p-values. No adjustment on multiplicity will be made. Continuous variables will be summarized by number of subjects, mean, standard deviation (SD), standard error (SE), median, Q1, Q3, minimum, and maximum. Categorical variables will be summarized by number and percentages of subjects. No imputation on missing data will be made, unless stated otherwise.

When the sample size and number of observations allow, the change from baseline over time will be analyzed using a generalized estimation equation (GEE) model that includes time as the categorical variable and adjusted for baseline measurement. The covariance structure that will be used for the GEE model is compound symmetry which specifies constant variance for the assessments and constant covariance between the assessments over time. If the number of observations are insufficient for analyses using a GEE model, a t-test will be performed for continuous variables and a 95% confidence interval (CI) of the proportion will be provided for binary variables.

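### The key secondary phosphorus responder rate shares its 2.5 mg/dL cut-off with a single-reading entry criterion, has no baseline term, and is tested only against 0%

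*SAP*

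**What the plan says.** - **Entry.** Protocol Section 7.3.1, criterion 3, sets two fasting biochemical limits: "Serum phosphorus < 2.5 mg/dL at Screening" and "TmP/GFR < 2.5 mg/dL at Screening". No repeat value is required.
- **Second pre-dose reading.** Protocol Table 2.1 schedules serum phosphorus again on Day -2. Under SAP Section 5.1 that value normally becomes baseline. Criterion 3 does not apply to it.
- **Endpoint.** SAP Section 8.6.2 takes each subject's mean phosphorus "at the mid-point of the dose interval (i.e., Weeks 2, 6, 14, and 22), as averaged across dose cycles between baseline and Week 24" and counts those above 2.5 mg/dL: "The number and proportion of subjects achieving mean serum phosphorus levels above the LLN (2.5 mg/dL [0.81 mmol/L]) will be summarized". It asks for no minimum rise and makes no reference to the subject's own baseline.
- **Inference.** The proportion gets a Wilson 95% interval, and a p-value "against 0% from the binomial test will also be provided". The Appendix 1 row lists only the descriptive summary and the Wilson interval. Section 8.1 adds: "All p-values will be presented as nominal p-values".
- **Objective.** Protocol Section 6: "The key secondary efficacy objective is to establish the effect of KRN23 treatment on increasing serum phosphorus levels in adults with XLH".
- **Related outputs.** Baseline phosphorus is summarised and listed (SAP Section 8.4). Change and percent change from baseline at the same mid-points are secondary endpoints, with a GEE model for change if it converges (SAP Sections 4.3 and 8.6.3.2).

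**The concern.** The objective is an increase, but the key secondary endpoint is a post-dose level in a single arm. Its threshold is the value that subjects had to be below, once, to get in. Someone whose usual level is close to 2.5 mg/dL can enter on one low reading, drift back to that level and be counted. Such a subject may already be above 2.5 mg/dL on Day -2.

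The test against 0% offers no protection. It takes the rate without drug effect to be exactly zero, which selection on one noisy reading does not guarantee. What is at stake is how much of the proportion, and of its p-value, is credited to KRN23.

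**Working it through.** **Inputs from the documents.** Entry below 2.5 mg/dL on one Screening reading; TmP/GFR below 2.5 mg/dL at Screening; responder if the mean of four readings exceeds 2.5 mg/dL; 14 subjects enrolled (SAP Section 3.1); null value 0%. The plan states no assumed rate or power for this endpoint, so there is no figure of its own to reproduce.

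**Assumed, because the documents give none.** Untreated mean 1.8 to 2.2 mg/dL, between-subject SD 0.30, within-subject SD s = 0.25, independent visits, no drug effect.

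**Step 1: the test against 0%.** P(X ≥ 1 | n = 14, p = 0) = 1 − (1 − 0)^14 = 0. One responder rejects the null. The Wilson interval for 1/14 is 1.3% to 31.5%. For contrast, with an assumed null of 5% or 10%, the smallest count giving an exact one-sided p ≤ 0.025 is 4 (p = 0.004) or 5 (p = 0.009).

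**Step 2: one subject with no drug effect.** For true mean μ, P(mean of four > 2.5) = 1 − Φ((2.5 − μ)/(s/2)).
- s = 0.2: 0.1% at μ = 2.2, 2.3% at 2.3, 15.9% at 2.4.
- s = 0.3: 2.3%, 9.1% and 25.2% at the same means.
- μ = 2.55, s = 0.2: the chance of passing Screening is Φ((2.5 − 2.55)/0.2) = 40%, and the chance of then being counted is 1 − Φ((2.5 − 2.55)/0.1) = 69%.

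**Step 3: the cohort.** Simulate true means, keep subjects with Screening phosphorus below 2.5, and count those whose four-reading mean exceeds 2.5. The third column also requires TmP/GFR below 2.5, modelled as tracking true phosphorus with independent SD 0.25 and an offset of 0 or −0.2 (the two ends of each range). The fourth column is 1 − (1 − p)^14 applied to the third.

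| Untreated mean | No-effect responders, phosphorus criterion only | With TmP/GFR criterion | At least one of 14 | Day -2 above 2.5, phosphorus criterion only |
|---|---|---|---|---|
| 1.8 | 0.8% | 0.5–0.7% | 7–9% | 2.7% |
| 2.0 | 3.0% | 1.8–2.4% | 22–29% | 6.9% |
| 2.1 | 5.2% | 3.0–4.2% | 35–45% | 10.0% |
| 2.2 | 8.4% | 4.7–6.6% | 49–62% | 13.9% |

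A wider grid (means 1.8 to 2.3, between-subject SD 0.2 to 0.3, within-subject SD 0.1 to 0.3, phosphorus criterion only) runs from near 0 to 14.8%.

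**Step 4: Day -2 as comparator.** A single reading is noisier than a mean of four, so with no drug effect it exceeds 2.5 more often: 2.7/0.8 ≈ 3.4 times as often at mean 1.8, and 13.9/8.4 ≈ 1.7 times at 2.2. It bounds the no-effect rate from above and does not estimate it. Restricting to Day -2 at or below 2.5 lowers the phosphorus-only rates at 2.0, 2.1 and 2.2 from 3.0, 5.2 and 8.4% to 1.8, 3.0 and 4.7%.

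**Step 5: a paired test.** Exact McNemar uses only subjects whose status changes. If c subjects move up and none move down, two-sided p = 2 × 0.5^c. Five shifts give 0.0625 and six give 0.031, where the 0% test needs one responder.

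**The case against.** The strongest reply is that the match is deliberate. The value 2.5 mg/dL is the lower limit of normal: being below it is part of the biochemical picture of the disease, and Protocol Section 7.4.3 gives exceeding it as the treatment strategy. The endpoint measures attainment of normal phosphorus, and the change-from-baseline endpoints measure the rise. Averaging four visits halves the within-subject SD if visits are independent, the TmP/GFR criterion removes some borderline subjects, and p-values are nominal. In a study of 14, a reader could match baseline values to responders from the listings.

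Most of this stands, and it is why the endpoint should stay. It also rules out three stronger readings:
- *Untreated subjects are counted as responders.* The documents do not support this. Every subject receives KRN23 (Protocol Section 7.4.2); the issue is a treated subject with no drug effect.
- *The plan makes no baseline comparison of phosphorus.* This is true of this endpoint only, as SAP Sections 8.4 and 8.6.3.2 show.
- *The shared cut-off is an internal contradiction.* It is not; the protocol explains the threshold.

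What the reply leaves open is that mean changes and a listing do not qualify the reported proportion, and neither replaces the test against 0%. It is also fair to say that a McNemar test compares one reading with a mean of four. That mismatch works against showing an effect, so it is acceptable if stated.

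**Conclusion.** The point holds as a modest limit on reading the responder proportion and its p-value as drug effect. The shared cut-off, the missing baseline term and the uninformative 0% null follow directly from the documents. The size does not. Under the assumptions above, and depending on how the TmP/GFR criterion acts, the no-effect rate is roughly 0.5% at an untreated mean of 1.8 mg/dL and 5 to 8% at 2.2 mg/dL.

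A reader might infer that a high response rate could be produced by selection alone. It could not. The Wilson lower limit for 13 of 14 is 68.5%, far above even the 14.8% at the top of the wider grid. Protocol Section 7.4.3 also reports that all subjects in the earlier extension study responded with increased phosphorus. The effect is on the share credited to the drug, chiefly if the observed proportion is middling or low.

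**What to change.** In SAP Section 8.6.2 and the matching Appendix 1 row, keep the endpoint and the Wilson interval and add, for the Full Analysis Set:

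1. The number and proportion of subjects above 2.5 mg/dL at baseline (Day -2), shown beside the mid-point proportion. Flag any subject whose baseline falls back to the Screening value, since entry holds that value below 2.5 mg/dL.
2. The paired 2×2 table of baseline (above or not above 2.5 mg/dL) by responder status, with an exact McNemar p-value, labelled nominal. Use this as the test of drug effect in place of reliance on the test against 0%.
3. A supportive responder rate among subjects at or below 2.5 mg/dL at baseline.
4. A sentence stating that the single-reading baseline rate is a conservative upper comparator, because one reading is noisier than a mean of four.

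The cost is a few sentences and one small table from data already scheduled, with no new samples or subjects. The supportive rate may be slightly less favourable, and there is one more nominal p-value. The paired test still has no control arm, so it shows change within subjects only.

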8.6.3 Secondary Efficacy Endpoints

8.6.3.1 Additional bone biopsy endpoints

Analysis for the following parameters will use the same analysis method for the primary endpoint:

- Additional histomorphometric parameters – including osteoid thickness (O.Th), osteoid surface/bone surface (OS/BS), and mineralization lag time (MLt)

The observed, change from baseline, and percent change from baseline values over time for the following parameters will be summarized.

- MAR, MS/BS, BFR and additional measures of bone formation and remodeling

A listing of the bone biopsy parameters will be provided.

A sensitivity analysis for bone biopsy parameters based on the bone osteomalacia severity at baseline may also be explored. A shift analysis from baseline to post-baseline for the bone osteomalacia severity based on the category reported in the EDC may also be performed.

8.6.3.2 Key PD

Descriptive summaries of the following secondary PD endpoints will be provided.

- Proportion of subjects achieving mean serum phosphorus levels above the LLN (2.5 mg/dL [0.81 mmol/L]) at the end of the dosing cycle (4 weeks after dosing), as averaged across dose cycles between baseline and week 24.
- Mean change from baseline and percent change from baseline in serum phosphorus at each mid-point of dosing cycle, as averaged across dose cycles between baseline and week 24.
- Mean change from baseline and percent change from baseline in serum phosphorus at each end of dosing cycle, as averaged across dose cycles between baseline and week 24.
- Time-adjusted area under the curve (AUC) of serum phosphorus between baseline and week 24.

Observed values and change from baseline, serum intact FGF23, percent change from baseline over time in serum phosphorus, 1,25(OH)₂D, and urinary phosphorus, TRP, TmP/GFR, and FEP will be summarized at each milestone analysis.

The change from baseline over time for key PD will be analyzed using the GEE model as described in Section 8.1, if the model converges.

A listing for the PD parameters will be provided.

Mean (\pm SE) PD-time plots may be presented for the PD parameters.

8.6.3.3 Bone turnover markers

Observed values, change and percent change from baseline over time in serum ALP and biochemical markers of bone turnover, including BALP, CTx, and P1NP, will be summarized at each milestone analysis. A listing will be provided for the biochemical markers of bone turnover.

The change from baseline over time for biomarkers will also be analyzed using the GEE model as described in Section 8.1, if the model converges.

Correlations may be used to assess the relationship between bone turnover markers and selected histomorphometric indices.

8.6.4 Exploratory Efficacy Endpoints

The number of active (non-healed) pseudofractures and/or fractures as defined by skeletal survey at baseline and the number and percentage of the baseline active pseudofractures/fractures which healed, partially healed, were unchanged or worsened at post-baseline visits will be summarized. New active pseudofractures and/or fractures identified at post-baseline visits will also be summarized.

The number of the subjects with baseline active pseudofractures and/or fractures and the number of those subjects who have changes from baseline to healed, partially healed, unchanged and worsened at post-baseline visits will be summarized. The number of subjects with new active pseudofractures and/or fractures at post-baseline visits will also be summarized.

For BPI (worst pain, pain severity and pain interference), BFI (worst fatigue, and global fatigue score), the observed values, change from baseline over time will be summarized. The change from baseline over time will also be analyzed using the GEE model as described in Section 8.1, if the model converges. Listings for the patient-reported outcomes will be provided.

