-  Both 2-hr and 24-hr urine will be used for measurements of urinary phosphorus, creatinine and calcium; 2-hr urine will be used for the derivation of TmP/GFR and TRP.
-  Only the BPI Question 3 (Worst Pain) will be administered at Screening for eligibility. The complete short-form BPI and BFI will be administered at all other indicated visits.
-  Administer BPI first followed by BFI. The BPI and BFI should be administered prior to the performance of any invasive procedures.
-  X-rays will be taken at locations pre-determined by skeletal survey (chest, lateral spine, right and left hand/wrist, right and left humerus, right and left radius/ulna, right and left femur/pelvis, right and left tibia/fibula, and right and left foot). If active pseudofracture(s) or fracture(s) are detected at baseline,

- targeted X-rays at that location will be obtained as indicated. During the Treatment Extension Period I, targeted x-rays will only be performed at clinic visit(s) to follow healing of any newly diagnosed fractures.
- 11 Vital sign measurements consist of seated systolic/diastolic BP measured in millimeters of mercury (mm Hg; 2 measurements separated by 15 minutes), HR (beats per minute), respiration rate (breaths per minute), and temperature in degrees Celsius (°C). Obtain at the beginning of the visit before any additional assessments are completed
- 12 Weight will be recorded in kilograms. Dose of study drug must be adjusted if weight increases by more than 20% from baseline.
- 13 Serum chemistry panels may include PD parameters (i.e. serum phosphorus), and safety parameters of interest (i.e. calcium) to avoid duplication of testing. Screening and Week 48 Day1 hematology will include Prothrombin time/Partial thromboplastin time (PT/PTT). ET hematology will include PT/PTT if a bone biopsy is also scheduled (if a subject discontinues the study between 24 and 48 weeks)
- 14 Urine pregnancy test for women of childbearing potential only. A serum pregnancy test will be performed in the event of a positive or equivocal urine pregnancy test result.
- 15 During the Open-Label Treatment Period (Weeks 1 – 48) and Treatment Extension Period I (Weeks 49-96) subjects will return to the clinic and/or have home health (HH) visits as indicated ( $\pm$  5 days). HH visits may also be conducted at the clinic depending on subject proximity to the investigational site and local availability of home health care resources.

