### **7.6.3 General Principles**

A general description of the statistical methods to be used to analyze the efficacy and safety of the study drug is outlined below. The analyses planned in this protocol will be expanded in the SAP to include detailed description. The SAP will be finalized and approved prior to the

database lock. Any deviations from the analyses described in the protocol and SAP will be noted in the final clinical study report.

The completeness of the data affects the integrity and accuracy of the final study analysis. Therefore, every effort will be made to ensure complete, accurate, and timely data collection, and to avoid missing data. In general, only subjects with a post-baseline efficacy evaluation will be included for that analysis. Missing data will be treated as missing and no statistical imputation method will be used unless stated otherwise. The procedures for handling missing, unused, or spurious data, along with the detailed method for analyses, will be presented in the SAP.

The statistical analyses will be reported using summary tables, figures, and data listings. For continuous variables, the mean, standard deviation, median, quartile, minimum, and maximum will be provided. For discrete data, the frequency and percent distributions will be provided.

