7 DATA SCREENING AND ACCEPTANCE

7.1 Handling of Missing and Incomplete Data

Missing clinical outcome data can occur for multiple reasons, including missed subject visits and measures with missing item scores. Missing and incomplete data will be identified through a review of tables and listings for this study. Missing and incomplete data will be identified for investigation, and possible resolution, by Data Management prior to the study database lock.

For all analyses, missing data will be treated as missing, unless otherwise specified. When a change from baseline is assessed, only subjects with a baseline and at least one post-baseline measurement will be included in the analysis.

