- ⁸ Only the BPI Question 3 (Worst Pain) will be administered at Screening for eligibility. The complete short-form BPI and BFI will be administered at all other indicated visits.
- ⁹ Administer BPI first followed by BFI. The BPI and BFI should be administered prior to the performance of any invasive procedures.
- ¹⁰ X-rays will be taken at locations pre-determined by skeletal survey (chest, lateral spine, right and left hand/wrist, right and left humerus, right and left radius/ulna, right and left femur/pelvis, right and left tibia/fibula, and right and left foot). If active pseudofracture(s) detected at baseline, targeted X-rays at

that location will be obtained as indicated. During the Extension Period, targeted x-rays will only be performed at clinic visit(s) to follow healing of any newly diagnosed fractures.

- 11 Vital sign measurements consist of seated systolic/diastolic BP measured in millimeters of mercury (mm Hg; 2 measurements separated by 15 minutes), HR (beats per minute), respiration rate (breaths per minute), and temperature in degrees Celsius (°C). Obtain at the beginning of the visit before any additional assessments are completed
- 12 Weight will be recorded in kilograms. Dose of study drug must be adjusted if weight increases by more than 20% from baseline.
- 13 Serum chemistry panels may include PD parameters (i.e. serum phosphorus), and safety parameters of interest (i.e. calcium) to avoid duplication of testing. Screening and Week 48 Day1 hematology will include Prothrombin time/Partial thromboplastin time (PT/PTT). ET hematology will include PT/PTT if a bone biopsy is also scheduled (if a subject discontinues the study between 24 and 48 weeks)
- 14 Urine pregnancy test for women of childbearing potential only. A serum pregnancy test will be performed in the event of a positive or equivocal urine pregnancy test result.
- 15 During the Open-Label Treatment Period (Weeks 1 – 48) and Treatment Extension Period (Weeks 49-96) subjects will return to the clinic and/or have home health (HH) visits as indicated (\pm 5 days). HH visits may also be conducted at the clinic depending on subject proximity to the investigational site and local availability of home health care resources.

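### Does the SAP's count of new pseudofractures and fractures need a stated imaged set, and do its change categories need a written rule?

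*SAP*

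**What the plan says.** SAP 8.6.4 first tabulates what became of the lesions that were active at baseline, in four categories: healed, partially healed, unchanged, worsened. It then adds new lesions, by lesion ("New active pseudofractures and/or fractures identified at post-baseline visits will also be summarized") and by subject ("The number of subjects with new active pseudofractures and/or fractures at post-baseline visits will also be summarized").

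For the analysis set, SAP 8.6 covers everything outside the bone biopsy endpoints with "All other efficacy analysis will be performed on the Full Analysis set at each milestone analysis".

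On imaging, the skeletal survey row appears only in the baseline schedule (Protocol Table 2.1; SAP Appendix 5). Weeks 12, 24, 36 and 48 carry targeted radiography. Protocol 7.5.1.4 and SAP 5.8 direct those films to the places the survey picked out. Protocol footnote 10 is narrower: "If active pseudofracture(s) or fracture(s) are detected at baseline", then "targeted X-rays at that location will be obtained as indicated". SAP footnote 10 names pseudofractures alone: "If active pseudofracture(s) detected at baseline, targeted X-rays at" the location concerned. In the extension periods, films follow a newly diagnosed fracture.

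On reading, Protocol 7.5.1.4 and SAP 5.8 describe two tasks for the blinded central reader: comparison with the baseline films against a checklist fixed in advance, and grading of pseudofractures as not healed, partially healed or fully healed.

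On missing data, SAP 7.1 says "For all analyses, missing data will be treated as missing, unless otherwise specified" and Protocol 7.6.3 says "In general, only subjects with a post-baseline efficacy evaluation will be included for that analysis".

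**The concern.** Ascertainment is lopsided. Healing is looked for at every site with an active baseline lesion, while new lesions are looked for only where a film is taken. A subject whose survey showed nothing has no scheduled film in Weeks 0 to 48 on the narrower readings, yet belongs to the Full Analysis Set. Protocol 7.5.1.2 expects better mineralization to prevent pseudofractures, so a low count could be taken as evidence of prevention when it partly reflects where the films were pointed.

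The second strand is the scale. SAP 8.6.4 glosses active lesions as non-healed. If that means the lowest of the reader's three grades, nothing lies below it, and the grade alone could never place such a lesion in the worsened category. The grades are also stated for pseudofractures only, while 8.6.4 covers fractures as well.

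**Working it through.** The plan states no figure for this endpoint, so there is nothing to reproduce. The checks below are counts and a comparison of texts.

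**1. Scheduled imaging.** Survey regions (Protocol 7.5.1.4, SAP 5.8): chest 1 + lateral spine 1 + 6 right/left pairs × 2 = 14. Targeted visits: 4. Repeating the survey at each visit would give 14 × 4 = 56 region-visits per subject. With k regions re-filmed at every visit, the share is 4k/56 = k/14. The documents do not give k, so it is assumed:

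| k | Region-visits | Share |
|---|---|---|
| 0 | 0/56 | 0% |
| 1 | 4/56 | 7.1% |
| 2 | 8/56 | 14.3% |
| 3 | 12/56 | 21.4% |

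These are shares of film fields, not detection probabilities, because regions are not equally likely to carry a lesion. Footnote 10 opens by listing all 14 regions in parentheses. Reading that as re-filming every region is possible, though less natural, and would give 56/56.

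**2. Does the treatment of un-filmed regions change the planned output?** Let x be the lesions identified on films taken. An un-filmed region adds 0 to x whether it is labelled not assessed or lesion-free. The lesion count is therefore the same under both conventions, and so is the number of subjects with a new lesion. Only a percentage would differ. For one affected subject among n, p = 1/n, with Wilson 95% limits

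(p + z²/2n ± z√[p(1−p)/n + z²/4n²]) / (1 + z²/n), z = 1.96.

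For n = 14: centre (0.0714 + 0.1372)/1.2744 = 0.164, half-width 0.151.

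| Denominator | p | Wilson 95% CI |
|---|---|---|
| 14 enrolled (taken as the Full Analysis Set) | 7.1% | 1.3% to 31.5% |
| 10 re-filmed (assumed) | 10.0% | 1.8% to 40.4% |
| 7 re-filmed (assumed) | 14.3% | 2.6% to 51.3% |
| 4 re-filmed (assumed) | 25.0% | 4.6% to 69.9% |

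The intervals are illustrative, since 8.6.4 plans none. They overlap almost entirely, so no firm rate could come from this table under any denominator.

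**3. Which denominator does the plan imply?** Section 8.6.4 asks for number and percentage for the fate of baseline lesions, but only for a summary of new lesions and a number of subjects. If a percentage is printed under the general rule in SAP 8.1, Protocol 7.6.3 generally limits the analysis to subjects with a post-baseline evaluation, and SAP 7.1 leaves missing data missing. The one outcome rule that turns absence of data into an unfavourable result is SAP 7.1.1, which applies to the key secondary endpoint. Nothing instructs anyone to score an un-filmed region as clear.

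**4. Can worsening be assigned?** Grades: 3. Reported categories: 4. Starting from not healed, the grade alone reaches unchanged, partially healed and healed, which is 3 of the 4. Two points limit this. Change from baseline is the subject of the reader's other task, the checklist comparison, which may record worsening directly. And no text equates active with the lowest grade: if a partially healed lesion counts as active, a move to not healed is worsening on the stated scale.

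**5. Wording differences.** The SAP is version 1.0 of 15 December 2016 and covers two amendments. The Protocol is Amendment 3 of 29 August 2017. The footnote mismatch fits that sequence. SAP 4.4 (pseudofractures), 8.6.4 (both lesion types) and Appendix 1 (healed and partially healed only, with a GEE entry that 8.6.4 does not plan) differ within one document, which looks like clerical drift.

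**The case for a change.** The strongest case for acting is that the remedy is cheap and the possible misreading favours the drug. A few lines in the SAP would put the number of subjects and regions imaged beside each count, mark un-filmed regions as not assessed, and state or cite the rule for worsening. No extra films or readers would be needed. The default missing-data rules speak of subjects and data, not of regions never scheduled for film, so they do not strictly settle the matter.

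Part of this stands. The count covers imaged sites only and should be described that way, and a reader of these two documents cannot see how a lesion comes to be called worsened.

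It does not show that the plan as written produces a wrong number. The count is of lesions identified, which is what 8.6.4 says it is. New lesions are not among the endpoints listed in SAP 4.4 or Protocol 7.6.4.4, and the stated objective is healing. A prevention claim would also fail for a separate reason: this is a single-arm study of about 14 subjects, and the documents give no comparison rate, so even complete surveys at every visit could not support it. Clinically apparent fractures are collected as adverse events at every site and home visit (Protocol 7.5.3.11).

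**Conclusion.** No change to the plan follows. This is missing detail in a descriptive, exploratory tabulation, of a kind analysts fill sensibly: footnote the new-lesion table as limited to imaged sites, give the number imaged at each visit, and take the change category from the reader's comparison with baseline. The wording differences over pseudofractures and fractures are clerical and can be tidied at any later revision.

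The size is small. The counts do not depend on how un-filmed regions are labelled. A percentage could range from 7.1% to 25.0% for one affected subject under the denominators tried. No hypothesis test in 8.6.4 concerns new lesions, and neither the OV/BV analysis nor any secondary endpoint uses these data.

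The conclusion rests on two assumptions: that the count is not presented as a whole-skeleton incidence, and that the reader's checklist, which is not reproduced in these documents, records change from baseline. If the checklist proved silent on worsening, the category would need a rule before the films are read, but the documents do not show that this is so.
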